2.4 Statistical methods

The statistical analysis was performed using the R Statistical Software (v4.1.2; R Core Team 2021). Categorical variables were expressed as counts and percentages, quantitative variables as mean (standard deviation) or as median and interquartile range (the 25th and 75th percentiles), in case of skewed distributions. The Chi-square or the Fisher's exact test was used to compare groups A and B for categorical variables. Student's t test or the Wilcoxon-Mann-Whitney test was calculated to compare groups A and B for continuous variables. Statistically significant differences were assessed using two-sided P-values below 0.05.

At multivariable analysis, logistic regression was used to model binary responses (IPR>Median vs IPR≤Median) as related to demographic, pharmacological, systemic, and clinical covariates that have resulted significant at univariable analysis.

Table 4. IPR comparative statistical analysis

	Group T (ozone therapy) (N=38)	Group C (controls) (N=79)	P-value
Inflammatory T1 (3–5 Days)[§]			
Mean (SD)	2.00 (0.870)	2.49 (0.875)	0,006
Median [Q1, Q3]	2.00 [1.00, 2.75]	2.00 [2.00, 3.00]	
Proliferative T2 (14 Days)[§]			
Mean (SD)	4.24 (1.51)	3.70 (1.02)	<0.001
Median [Q1, Q3]	5.00 [4.00, 5.00]	4.00 [3.00, 4.00]	
Remodelling T3 (6 Weeks)[§]			
Mean (SD)	3.00 (0)	2.96 (0.192)	0,230
Median [Q1, Q3]	3.00 [3.00, 3.00]	3.00 [3.00, 3.00]	
IPR_Total Process[§]			
Mean (SD)	9.37 (1.79)	9.15 (1.38)	0,275
Median [Q1, Q3]	9.50 [9.00, 10.00]	9.00 [8.00, 10.00]	

[§]Wilcoxon signed-rang test

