On the day of the surgery (T0), the surgical protocol for Group B included the following steps: superficial local anesthesia using EMLA® cream, loco-regional anesthesia, incision and flap debridement, extraction of teeth with a poor prognosis, osteoplasty, achieving hemostasis, and suture.

Healing Evaluation and follow-up

In both groups, patients underwent additional follow-up visits at T1 (3-5 days), T2 (14 days), and T3 (6 weeks) post-extraction to meticulously monitor surgical wound healing by Inflammatory Proliferative Remodeling (IPR) Wound Healing Scale (Table 4) [20], and to record pain intensity by the NRS scale for enhanced ease of use, rather than the originally planned VAS scale [22].

The IPR scale provided a comprehensive assessment of wound healing through distinct subscales, each ranging from 0 to 1, resulting in a total score ranging from 0 to 16. These subscales evaluated the inflammatory response, proliferative response, and remodeling process. At the end of the follow-up period, the total IPR score was computed, with scores spanning from 0 to 16. Scores of 0-4 denoted poor healings, scores of 5-10 indicated acceptable healing, while scores of 11-16 suggested excellent healing.

Table 4. IPR (Inflammatory Proliferative Remodeling) Scale [21]

T/PHASE	Parameter	Score 0	Score 1	Total score
INFLAMMATORY T: 3-5 DAYS	Bleeding, spontaneously or on palpation	Yes	No	/8
	Granulation tissue	Yes	No	
	Haematoma	Yes	No	
	Tissue colour	Redder or whiter than opposite side tissue	Like the opposite side tissue	
	Incision margins	Incomplete flap closure/fibrin clot/partial necrosis/complete necrosis	Complete flap closure/fine fibrin line	

	Suppuration Edema NRS (1–10) Pain NRS (1–10)	Yes NRS 6–10 NRS 6–10	No NRS 1–5 NRS 1–5	
PROLIFERATIVE T: 14 DAYS	Re-epithelialisation	Partial	Complete	/5
	Tissue colour	Redder or whiter than opposite side tissue	Like the opposite side tissue	
	Scar	Scar wider than 2 mm/contour irregularity	No scar/scar less wide than 2 mm/contour regularity	
	Suppuration Pain NRS (1–10)	Yes NRS 6–10	No NRS 1–5	
REMODELING T: 6 WEEKS	Scar	Scar wider than 2 mm/contour irregularity	No scar/scar less wide than 2 mm/contour regularity	/3
	Tissue colour	Redder or whiter than opposite side tissue	Like the opposite side tissue	
	Pain NRS (1–10)	NRS 6–10	NRS 1–5	
TOTAL PROCESS				/16

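### The only multivariable model splits IPR at the sample median without a stated reason; if IPR is the total score, the cut falls inside the protocol's own acceptable band and discards ordinal information.

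*Combined protocol and SAP*

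**What the plan says.** Healing Evaluation and follow-up defines the IPR scale as items "each ranging from 0 to 1, resulting in a total score ranging from 0 to 16". The scale table gives the inflammatory phase (T1, days 3-5) up to 8 points, the proliferative phase (T2, day 14) up to 5 and the remodelling phase (T3, 6 weeks) up to 3. The same section sets clinical bands for the total: "Scores of 0-4 denoted poor healings, scores of 5-10 indicated acceptable healing, while scores of 11-16 suggested excellent healing".

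Section 2.4 does not use these bands. Its one multivariable analysis states that "logistic regression was used to model binary responses (IPR>Median vs IPR≤Median", related to covariates that were significant at univariable analysis. The section does not say whether IPR here is the total or a phase score, whether the median is pooled or per group, or why the median was chosen. It does not say whether treatment group is among the covariates.

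The IPR results table in section 2.4 gives the total in the ozone group as median and quartiles "9.50 [9.00, 10.00" (N=38), and in controls as median 9, quartiles 8 and 10 (N=79).

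**The concern.** A cut at the sample median defines response by rank within this sample and not by a healing state. The protocol supplies healing states, and the model ignores them. If the cut falls within one of the bands, two patients whom the protocol classes alike are coded as success and failure, and the odds ratios cannot be read as odds of better healing on the protocol's own terms. The cut would also move in another cohort. Reducing a 17-level score (0 to 16) to two levels also loses information about how strongly any covariate relates to healing.

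A further feature comes from adding the phases. Only 8 points remain after T1, so a low T1 score can rule out response before the later visits take place.

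**Working it through.** Assumptions: IPR in the model is the total score; the cut is the sample median; scores are whole numbers; quartiles follow the R default (a Q3 of 2.75 with N=38 fits that definition).

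**1. Where the cut falls**

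- Ozone total, N=38. Q1 lies at position 1 + 37×0.25 = 10.25 and Q3 at 1 + 37×0.75 = 28.75. Q1 = 9 makes the 10th and 11th values 9. The median of 9.5 makes the 19th value 9 and the 20th value 10. Q3 = 10 makes the 28th and 29th values 10.
- So at most 9 ozone patients score 8 or less, and exactly 19 score 9 or less.
- Control total, N=79. A median of 9 makes the 40th value 9. At most 39 score 8 or less, and at least 40 score 9 or less.
- Pooled, N=117. At most 9 + 39 = 48 are at 8 or less and at least 19 + 40 = 59 are at 9 or less, so the 59th value is 9.
- With whole-number scores, a median of 9 or of 9.5 gives the same split: 10 or more versus 9 or less.

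Scores 5-9 therefore count as non-response, and 10 counts as response together with 11-16, although 5-10 is one protocol band. In the ozone group 38 − 19 = 19 patients exceed the cut. The 20th to 29th values are all 10, so at least 10 of those 19 are only acceptable on the protocol's scale and at most 9 can be excellent.

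**2. What is settled at T1**

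T2 and T3 add at most 5 + 3 = 8. A T1 score of 1 or less gives a total of at most 1 + 8 = 9, so the cut cannot be exceeded.

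- Ozone T1: mean 2.00, SD 0.870, "2.00 [1.00, 2.75". The sum is 76, and the squared deviations from 2 add to 37×0.870² ≈ 28. Q1 = 1 means at least 11 patients score 1 or less; Q3 = 2.75 means exactly 28 score 2 or less and 10 score 3 or more. Only one distribution fits: 12, 16, 8 and 2 patients scoring 1, 2, 3 and 4. Check: 12 + 32 + 24 + 8 = 76, and 12×1 + 8×1 + 2×4 = 28.
- So 12/38 (32%) cannot exceed the cut.
- Control T1: mean 2.49, SD 0.875, "2.00 [2.00, 3.00". The sum is 197 and the sum of squares 551. Enumeration gives 292 fitting distributions, with 0 to 10 patients at 1 or less (at most 10/79 = 13%). One that reaches 10 is 10, 30, 29 and 10 patients scoring 1, 2, 3 and 4: sum 10 + 60 + 87 + 40 = 197, squares 10 + 120 + 261 + 160 = 551.
- Requiring the printed T1 P-value of 0.006 as well narrows the control range to 1 to 8.

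**3. Consistency of the rows**

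- Ozone phase sums: 76 + 161 + 114 = 351, and 351/38 = 9.24. The printed total mean is 9.37, which needs a sum of 356. Rounding does not explain the 5-point gap.
- Control phase sums: 197 + 292 + 234 = 723, and 723/79 = 9.15, as printed.

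**4. Information lost by the split**

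Simulation with rounded normal totals, SD 1.5 and groups of 38 and 79, two-sided 0.05, 3000 runs. The differences of 0.8 and 1.0 are assumed; 0.22 is the observed 9.37 − 9.15.

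| Difference in total | Rank test | Median split |
|---|---|---|
| 0.22 | about 11% | about 10% |
| 0.8 | about 73% | about 58% |
| 1.0 | about 89% | about 75% |

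Repeat runs, one with the control mean at the printed 9.15, moved these figures by up to about three points and left the gap at 0.8 at about 15 or 16 points.

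**The case against.** **The arms are already compared without a split.** Section 2.4 compares groups on continuous variables with a t test or a Wilcoxon-Mann-Whitney test, and the results table applies a rank test to the total (P = 0.275). This stands. The loss concerns the covariate model only, and section 2.4 does not say that treatment is in it. The two-group power figures therefore illustrate what a split costs; they are not the power of the plan's arm comparison.

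**The power scenarios are larger than what was seen.** This also stands. Differences of 0.8 and 1.0 are about four times the observed 0.22 or more, and at 0.22 almost nothing is lost.

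**A reader might infer that the rule works against ozone**, because more ozone patients are ruled out at T1. The documents do not support that. Exactly 19/38 (50.0%) of the ozone group exceed the cut. In controls the median of 9 allows at most 39/79 (49.4%), and 21 to 39 if the 59th and 60th values are both 10. Ozone is not below control at this cut. Low T1 scores are also a legitimate part of a total in which inflammation carries 8 of 16 points.

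**Early settlement comes from summing the phases, not from the median.** Agreed. A cut at the protocol's excellent band (11 or more) needs a T1 score of at least 3, so 28/38 ozone patients and 40 to 58 of 79 controls would be ruled out at T1. Early settlement is therefore no argument for that cut.

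**The total is only assumed to be the outcome.** True. If a phase score was modelled, the arguments from the bands and from T1 fall away, and the unexplained, sample-dependent split remains.

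**Conclusion.** The concern holds as a choice of analysis that should be improved. The only multivariable model uses an unexplained, sample-dependent split. If IPR is the total score, the split is 10 or more versus 9 or less and cuts through the 5-10 band, so its odds ratios do not correspond to a healing class that the protocol defines. The cost in information is about 15 percentage points of power at an assumed 0.8-point difference with SD 1.5, and negligible at the observed difference.

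The counts of 12/38 ozone and 0-10/79 controls unable to exceed the cut describe how the summed score behaves. They rest on the printed T1 row, which is consistent within itself. Combining them with the ozone total row is conditional until the 9.24 and 9.37 are reconciled. They are not evidence of bias against ozone, and nothing here disturbs the unadjusted rank comparison of the total.

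**What to change.** In section 2.4:

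- Replace the median split with a proportional-odds (ordinal) model of the 0-16 total, with the same covariates.
- State that the total is the modelled outcome.
- Report the number of patients in each protocol band (0-4, 5-10, 11-16) by arm, beside the phase-specific results.
- Do not substitute a binary cut at 11 or more, for the reason given above.
- Reconcile the ozone phase rows with the ozone total row before the model is re-run.

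The cost is one re-run on data already held, a few words of text and a small table. The downside is that the proportional-odds assumption has to be checked and the result of that check reported.

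### The only adjusted analysis splits an unnamed IPR score at an unspecified median and selects terms by significance, so an adjusted ozone effect is not assured

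*Combined protocol and SAP*

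**What the plan says.** Section 2.4 compares the arms by unadjusted tests and then describes a single multivariable step, in which "logistic regression was used to model binary responses (IPR>Median vs IPR≤Median"). The explanatory terms are "demographic, pharmacological, systemic, and clinical covariates that have resulted significant at univariable analysis". The threshold for significance is given as "Statistically significant differences were assessed using two-sided P-values below 0.05".

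The only univariable tests described are between-arm ones; the chi-square or Fisher test, for instance, "was used to compare groups A and B for categorical variables". The IPR comparative table in the same section reports four scores (T1, T2, T3 and total). The logistic sentence does not say which of them is split, or whether the median is pooled. No logistic result is shown.

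**The concern.** The stated aim is to compare extraction protocols with and without ozone. An adjusted model serves that aim only if treatment is in it. Under this rule, treatment is either unmentioned or has to earn its place by P-value like any other term. Three problems follow.

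- **Selection.** A term kept because it was significant has an estimate biased away from zero, and a term that was not significant has no adjusted estimate.
- **Outcome.** Splitting a 0-16 score discards information, and with four candidate scores the model is not identified.
- **Undefined screen.** Univariable could mean association with the split outcome (the ordinary reading) or the between-arm tests that the section describes. The two give different models.

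Adjustment is not idle here. Patient type differs between the arms in Table 2, with 31.6% of ozone patients and 53.2% of controls in the ost category.

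**Working it through.** **The plan's own figures.** With no logistic result printed, there is none to reproduce. The T3 comparison can be checked. With 38 ozone patients at 3, 76 controls at 3 and 3 controls at 2, the control mean is (76×3 + 3×2)/79 = 2.96 and the SD 0.192, as printed. The rank-sum P is 0.2297, against 0.230 printed.

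**Inputs.** Arm sizes are 38 and 79. Medians and quartiles come from the IPR comparative table: total "9.50 [9.00, 10.00" for ozone and "9.00 [8.00, 10.00" for controls; T1 "2.00 [1.00, 2.75" and "2.00 [2.00, 3.00". Scores are whole numbers. Quartiles are read as R's default (type 7), at position 1 + p(n − 1) in the ordered data. Write x(k) for the k-th smallest score.

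**Where the total-score cut falls.**
- Ozone: the first quartile of 9 (position 10.25) makes x(10) = 9, so at most 9 patients score 8 or less. The median of 9.5 is the mean of x(19) and x(20), which must be 9 and 10, so exactly 19/38 score 10 or more.
- Controls: the median is x(40) = 9, so at most 39 exceed 9. The third quartile is the mean of x(59) and x(60) and equals 10, so x(60) is at least 10 and at least 20 exceed 9.
- Pooled: the median is the 59th of 117. At most 9 + 39 = 48 patients score 8 or less, and at least 19 + 40 = 59 score 9 or less, so the median is 9.

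The cut therefore separates 9 from 10, although both fall in the protocol's acceptable band (5-10).

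**Treatment against the split total.** With k controls above 9, the uncorrected chi-square is 117 × [19(79 − 2k)]² / [38 × 79 × (19 + k) × (98 − k)]:
- k = 20: 117 × 741² / (38×79×39×78) = 7.03, P = 0.008
- k = 24: 117 × 589² / (38×79×43×74) = 4.25, P = 0.039
- k = 25: 117 × 551² / (38×79×44×73) = 3.68, P = 0.055
- k = 39: 117 × 19² / (38×79×58×59) = 0.004, P = 0.95

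The printed rank-test P of 0.275 does not narrow this. Datasets matching the printed mean, SD and quartiles were enumerated (974 ozone sets; 18,479 control sets with scores 5-13). Every k from 20 to 39 occurs with a rank-sum P between 0.2745 and 0.2755.

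**All four scores, split at the pooled median.**

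| Score | Cut | Ozone above | Controls above | Split P | Printed P, undivided |
|---|---|---|---|---|---|
| T1 | 2 | 10/38 | 21-35/79 | 0.06-0.98 | 0.006 |
| T2 | 4 | 26-27/38 | 10-19/79 | <0.00001 | <0.001 |
| T3 | 3 | 0/38 | 0/79 | no model | 0.230 |
| Total | 9 | 19/38 | 20-39/79 | 0.008-0.95 | 0.275 |

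At T1 only one ozone dataset fits: 12, 16, 8 and 2 patients at scores 1, 2, 3 and 4. Of the control sets that fit (292), those giving a rank-sum P of 0.0055-0.0065 have 21 to 35 patients above 2. The split thus loses a difference, here against ozone, that the undivided score shows. At T3 the median of 3 is the subscale maximum, so nobody can exceed it.

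**If the screen is the between-arm tests.** Patient type (22/4/12 v 35/2/42) gives P = 0.034 and enters. Risk category (22/16 v 35/44), which is patient type collapsed to two levels, gives P = 0.168 and does not. Age (t test) gives 0.169 and sex 0.296.

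**Power and bias (simulation, 2,400 trials per cell).** Total scores were drawn from rebuilt datasets. The gain is an assumption, since the documents give no target effect. Patient type and age were in each model with no assumed effect.

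| Mean gain | Score shape | Proportional odds | Median split |
|---|---|---|---|
| 0.5 | control | 45% | 35% |
| 0.5 | ozone | 34% | 35% |
| 1.0 | control | 95% | 85% |
| 1.0 | ozone | 87% | 87% |

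At zero effect, rejection was 5.0-5.4% for proportional odds and 5.0-6.2% for the split. At the 0.5-point gain, treatment passed a split-outcome screen in about 37% of trials. Its mean log odds ratio was then 1.12-1.17, against 0.67-0.70 over all trials. As odds ratios that is about 3.1-3.2 (exp 1.12, exp 1.17) against about 2.0 (exp 0.67, exp 0.70).

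**The case against.** The strongest reply is that covariates may mean terms added to a treatment term already in the model, or that the model was only a search for prognostic factors. No logistic estimate is printed, so none is shown to be biased. Assignment is described as random, and the unadjusted rank tests already address the comparison. This limits the consequence: nothing here shows that ozone was left out. It does not repair the rule, which as written does not guarantee that treatment is in the model.

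The total is also the natural reading of IPR, since it alone has interpretive bands. That is fair, and it makes the phase-score rows secondary. For the total itself, however, the printed figures still leave entry of treatment undetermined.

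The ends of the P range are bounds, not likely values. Only 45 of the 18,479 fitting control sets have 20 patients above 9, and counts of 20-24 make up about 16% of sets (unweighted, so not a probability). With the Yates correction the limit for P below 0.05 moves from 24 to 23 controls; Fisher's test leaves it at 24. None of this makes entry assured.

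Finally, the split costs no power for ozone-shaped scores, and any replacement is now post hoc. Both points stand. The case for change rests mainly on forcing treatment in and dropping the significance screen.

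**Conclusion.** The concern holds and should be fixed. The text establishes the main point: the only adjusted analysis does not secure an adjusted ozone effect, does not identify its outcome, and chooses its terms by P-value. For the total score, the split P for treatment lies between 0.008 and 0.95, and falls below 0.05 only if 20 to 24 controls exceed 9. Under a split-outcome screen, treatment would enter at T2, fail at T1 and have no model at T3.

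The counts assume type 7 quartiles, a pooled median and an uncorrected chi-square. The bias and power figures also rest on an assumed effect and rebuilt scores. The printed total is taken as it stands, although the ozone phase means sum to 2.00 + 4.24 + 3.00 = 9.24, not the printed 9.37 (controls: 2.49 + 3.70 + 2.96 = 9.15, as printed). The finding does not touch the unadjusted comparisons.

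**What to change.** First state three facts: which IPR score and which median were used, what univariable meant, and whether group was in the fitted model. Check the ozone total against its phase scores. Then replace the rule with wording such as:

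> Total IPR (0-16) is modelled by proportional-odds regression. Treatment group is always included, with a fixed covariate set chosen without significance screening (for example age, and either patient type or risk category, not both). The adjusted ozone effect is reported with its 95% CI. This analysis was specified post hoc, after the unadjusted results were known.

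Keep the median-split model, with treatment forced in, as a sensitivity analysis at most.

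The cost is SAP wording and one re-run on collected data. The proportional-odds assumption needs checking. The onc2 coefficient will be imprecise if three-level patient type is used, with 4 + 2 = 6 such patients. The covariates are chosen after results are known, hence the post hoc label. A power gain over the split is not assured for every score shape.

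### Results Table 4, ozone column: the T1, T2 and T3 means add to 351 points (mean 9.24), but the printed IPR total implies 356 (mean 9.37)

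*Combined protocol and SAP*

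**What the plan says.** The IPR scale table in Section 2.3 scores every item 0 or 1, with eight items at T1 (3–5 days), five at T2 (14 days) and three at T3 (6 weeks). The text describes "distinct subscales, each ranging from 0 to 1, resulting in a total score ranging from 0 to 16" and adds: "At the end of the follow-up period, the total IPR score was computed, with scores spanning from 0 to 16". A higher score means better healing.

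The results table in Section 2.4, "Table 4. IPR comparative statistical analysis" (the scale table carries the same number), has columns headed "Group T (ozone therapy) (N=38") and "Group C (controls) (N=79"). It prints these means (SD):

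| Row | Ozone | Control | P |
|---|---|---|---|
| T1 | 2.00 (0.870) | 2.49 (0.875) | 0.006 |
| T2 | 4.24 (1.51) | 3.70 (1.02) | <0.001 |
| T3 | 3.00 (0) | 2.96 (0.192) | 0.230 |
| Total | 9.37 (1.79) | 9.15 (1.38) | 0.275 |

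No row has its own N, and no missing scores are mentioned. For continuous variables the text of Section 2.4 says the "Wilcoxon-Mann-Whitney test was calculated to compare groups A and B for continuous variables" (with Student's t test as the alternative), while the table footnote says "Wilcoxon signed-rang test". The section also states that "logistic regression was used to model binary responses", with IPR split at its median.

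**The concern.** The mean of a sum equals the sum of the means over the same patients. The ozone phase means add to 9.24, not 9.37, so at least one figure in that column is wrong if all 38 patients count in every row.

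This is the only outcome table. Depending on the faulty row, the plan misstates the overall difference, the T2 advantage of ozone or the T1 advantage of control. If patients' totals are wrong, and not only their printed mean, the binary outcome of the regression can change as well.

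A secondary point is the footnote. A signed-rank test needs paired data and cannot compare 38 patients with 79 other patients.

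**Working it through.** **Inputs.** Means, SDs, medians, quartiles and group sizes come from the results table in Section 2.4, and the item structure from the IPR scale table in Section 2.3. Items are 0 or 1, so each patient's score is a whole number and each group sum is a whole number S with S/N rounding to the printed mean.

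**Control column first (N = 79).** The only fitting sums are 197 (2.49), 292 (3.70) and 234 (2.96). They add to 723, and 723/79 = 9.152, which is the printed 9.15. The total was therefore formed by adding the phases.

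**Ozone column (N = 38).** The only fitting sums are:
- T1: 76/38 = 2.00
- T2: 161/38 = 4.237
- T3: 114/38 = 3.00
- Total: 356/38 = 9.368

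The phases give 76 + 161 + 114 = 351, and 351/38 = 9.237. The gap is 5 points, or 5/38 = 0.13 in the mean. Rounding each phase mean by up to 0.005 allows only 9.225 to 9.255. T3 is at its maximum with SD 0, so it cannot be the short row.

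**Could missing scores explain it?**
- From N = 20 to 38, only N = 38 allows both 4.24 and 9.37 as means of whole-number scores.
- For the total row alone, a median of 9.50 needs an even N. A mean of 9.37 is impossible at N = 36 or 34. The next even candidates are 32 (300/32 = 9.375, if rounded down) and 30 (281/30), so at least six patients would have been dropped under a header of 38.
- If only T2 scores were missing, the missing patients must supply 166 − S points, at most 5 each. N = 37 needs 166 − 157 = 9 from one patient, N = 34 needs 166 − 144 = 22 from four, and N = 33 needs 166 − 140 = 26 from five. None is possible. At least nine patients would have to be missing.

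**Which test was run?** The control T3 figures (sum 234, SD 0.192) require three scores of 2 and 76 of 3. Against 38 ozone scores of 3, a rank-sum test gives P = 0.2297, matching 0.230 (N = 37 gives 0.236). T1 and T2 are also compatible with a rank-sum test. All P-values here use the normal approximation with tie and continuity correction.

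**Size, one wrong row at a time, five points moved in the direction that closes the gap.**

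*Total wrong (356 to 351).* The difference goes from 9.37 − 9.15 = 0.22 to 9.24 − 9.15 = 0.09 (0.085 before rounding). In sampled score sets with five points removed, P was 0.27 to 0.73. In a different sample, of sets summing to 351 that keep the printed SD and quartiles, it was 0.07 to 0.54. For the regression, assume the outcome is the total and the median is taken over all 117 patients. The printed quartiles then force a median of 9 and exactly 19 of 38 ozone patients above it. Removing five points leaves 14 to 19.

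*T2 wrong (161 to 166).* The difference goes from 0.54 to 166/38 − 292/79 = 4.368 − 3.696 = 0.67. Four ozone and 102 control score sets fit the printed row. After five points are added, P is at most 0.00012.

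*T1 wrong (76 to 81).* The difference in favour of control goes from 0.49 to 197/79 − 81/38 = 2.494 − 2.132 = 0.36. One ozone distribution fits the printed row: 12 ones, 16 twos, 8 threes and 2 fours. Of 129 fitting control sets (scores 0–5), 28 give P = 0.006. There are 83 ways to add five points, so 83 × 28 = 2,324 combinations:
- Over all of them, P runs from 0.007 to 0.097 and is at or above 0.05 in 289.
- One patient corrected by five points gives P of 0.008 to 0.026.
- Five patients corrected by one point each give 0.013 to 0.097, and all 289 lie among these 1,288 combinations.
- Five patients moved from 2 to 3 gives 0.067 to 0.097 in all 28 control sets.

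**The case against.** The strongest reply is that the three rows are not equally suspect. With a T1 sum of 81 or a T2 sum of 166, no set of 0–5 scores reproduces that row's printed SD and quartiles. A total of 351 can keep its SD of 1.79 and its 9.50 [9.00, 10.00]. One misprinted mean, 9.37 for 9.24, would then reconcile the whole column. No patient's total would change, and the regression and the P-value of 0.275 would stand. On that reading this is a small erratum in a comparison already reported as non-significant.

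The feasibility result is correct, and it makes a misprinted total mean the most economical explanation. It does not settle the matter. Mean, SD and quartiles are computed from the same scores, so a data or coding error in T1 or T2 would shift them together.

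It is also fair that the ranges above are not bounds. They assume one faulty row and changes in one direction, and offsetting errors are not covered. The T1 combinations fit the printed row only before correction; for example, moving five patients from 2 to 3 changes the third quartile from 2.75 to 3.00. Counts of combinations are not probabilities. Finally, the footnote is a separate labelling point and adds no weight to the arithmetic.

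**Conclusion.** The concern holds. With 38 patients in every row, the ozone column cannot be right as printed: the phases give 351 points (9.24) and the total gives 356 (9.37). The inconsistency rests only on additive whole-number scoring, which Section 2.3 defines and the control column confirms, and on the N in the header. Different denominators by row cannot be fully excluded, but none is reported.

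The documents do not show which row is wrong. A five-point correction leaves the T2 conclusion unchanged and left the total non-significant in every set sampled. The T1 conclusion survives most of the corrections examined but not all. The effect on the regression ranges from nothing to five ozone patients changing category. The footnote is most likely a wrong label and not a wrong analysis. The point should be fixed because it concerns a figure in the only outcome table.

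**What to change.** Re-derive T1, T2 and the total for the 38 ozone patients from the item-level records. Correct the wrong row or rows, including SD and quartiles, and print N for each row. Rerun the rank-sum test only for a row whose scores change, and the median-split regression only if any patient's total changes. Check the analysis code and, if it confirms the rank-sum test, change the footnote to Wilcoxon-Mann-Whitney.

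The cost is a data check on 38 patients and a few reruns. The authors should expect that a stated difference may become more or less favourable to ozone.

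### The printed day 3-5 IPR scores are implausibly low under the plan's own scoring key; the coding must be checked item by item, because the total comparison depends on it, and the ozone total does not add up.

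*Combined protocol and SAP*

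**What the plan says.** Under Healing Evaluation and follow-up, the IPR scale table scores each item 0 for the unfavourable finding and 1 for the favourable one. For "Bleeding, spontaneously or on palpation", for example, yes scores 0 and no scores 1. There are 8 items at T1 (3-5 days), 5 at T2 (14 days) and 3 at T3 (6 weeks), so the total runs from 0 to 16. Higher is better: 0-4 is poor, 5-10 is acceptable, and "scores of 11-16 suggested excellent healing".

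Section 2.4 prints the results (this table is also numbered 4) for "Group T (ozone therapy) (N=38") and "Group C (controls) (N=79"):

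| Row | Ozone, mean (SD) | Control, mean (SD) | P |
|---|---|---|---|
| T1 | 2.00 (0.870) | 2.49 (0.875) | 0.006 |
| T2 | 4.24 (1.51) | 3.70 (1.02) | <0.001 |
| T3 | 3.00 (0) | 2.96 (0.192) | 0.230 |
| Total | 9.37 (1.79) | 9.15 (1.38) | 0.275 |

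The T1 median and quartiles are "2.00 [1.00, 2.75"] for ozone and 2.00 [2.00, 3.00] for control. The same section dichotomises the total at its median as the response for the logistic model.

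**The concern.** Read by the key, about 75% of T1 items were unfavourable in the ozone arm (6.00 of 8) and about 69% in the control arm (5.51 of 8), under antibiotic and chlorhexidine cover. Ten days later most patients are at or near the top of the scale. The key also makes ozone significantly worse at T1 and significantly better at T2. If T1 had been entered as a count of adverse signs, both oddities would disappear: patients would have 2 to 2.5 signs each, with ozone better at both visits.

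The direction of the T1 result, the total, the healing bands and the logistic response all depend on which reading is correct. The documents give no item-level data and do not say that T1 was counted the other way.

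**Working it through.** **Inputs.** Means, SDs, quartiles and arm sizes come from the section 2.4 results table; item direction and counts come from the IPR scale table. I assume that every patient was scored at every visit and that quartiles follow R's default (type 7), since section 2.4 names R.

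**1. Reproducing the printed P-values.** The text of section 2.4 names the unpaired test ("Wilcoxon-Mann-Whitney test was calculated to compare groups A and B for continuous variables"), while the table footnote names "Wilcoxon signed-rang test", which reads as a paired test. The unpaired rank-sum test on T3 (38 scores of 3, against 76 of 3 and 3 of 2) gives 0.230, as printed. Score sets rebuilt to match the printed summaries give T1 P = 0.0016 to 0.0063, T2 P < 0.001 and total P = 0.12 to 0.55 (median 0.30). These ranges contain the printed values, so the table appears to hold unpaired results.

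**2. The ozone T1 distribution.**
- Sum of scores: 38 × 2.00 = 76.
- Sum of squares: 37 × 0.870² + 38 × 2.00² = 28.0 + 152 = 180.
- The upper quartile lies 0.75 of the way from the 28th to the 29th ordered score. With integers, 2.75 requires these to be 2 and 3, so exactly 28 patients score 2 or less.
- Enumerating all integer distributions on 0-8 leaves one: 12 patients at 1, 16 at 2, 8 at 3, 2 at 4. Check: 12+32+24+8 = 76 and 12+64+72+32 = 180.

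**3. What this means under the key.** A score of 2 or less means at least 6 of 8 items unfavourable. Only five T1 items are something other than suppuration, oedema NRS 6-10 or pain NRS 6-10. Each of the 28 ozone patients (74%) therefore had at least one of those three. The control median of 2 is the 40th of 79 ordered scores, so at least 40 controls were in the same position.

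**4. How T1 entered the total.** Each printed mean fixes an integer sum.
- Control: 197 + 292 + 234 = 723, and 723/79 = 9.15, the printed total. T1 was added as printed.
- Ozone: 76 + 161 + 114 = 351, and 351/38 = 9.24. The printed 9.37 needs 356. The gap of 5 points (0.13) exceeds the largest rounding error, 0.02.

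**5. If all T1 items were reversed (8 − T1), on the phase-mean basis.**
- Ozone: 6.00 + 4.24 + 3.00 = 13.24.
- Control: 5.506 + 3.696 + 2.962 = 12.16.
- The difference goes from 0.09 (9.24 − 9.15) to 1.07.

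| SDs used for the reversed total | Ozone, control | Welch P |
|---|---|---|
| Printed total SDs | 1.79, 1.38 | 0.002 (t = 1.07/0.329 = 3.26) |
| Covariance implied by printed SDs | 1.69, 1.33 | 0.001 |
| Largest possible (sum of phase SDs) | 2.38, 2.087 | 0.021 (t = 1.07/0.452 = 2.37) |

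Rank-sum tests on 6,000 pairs of rebuilt data sets gave P of at most about 0.0002 after reversal. Those sets use the 9.24 basis, because the printed 9.37 cannot be met from the phase means. They also restrict control T1 to at most 4 and control T2 to at least 1.

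**The case against.** A reader might infer that the table contradicts its key, or that T1 was miscoded and ozone in truth improves the total. The documents support neither. Scores of 1 to 4 lie inside the permitted 0-8 range, so nothing printed breaches the key. T1 is an inflammatory subscale scored days after flap surgery, extraction and osteoplasty. Five of its items can lose the point through ordinary early findings such as a fibrin clot or a colour difference, and a staged scale may start low and recover.

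Two further facts count against assuming whole-scale reversal:
- A count of adverse signs would be expected to covary negatively with later favourable scores. The total variance minus the phase variances is slightly positive in both arms: 3.204 − 0.757 − 2.280 = 0.17 for ozone and 1.904 − 0.766 − 1.040 − 0.037 = 0.06 for control. This is weak evidence, since it is near zero and the ozone column does not add up.
- The four distributions that fit ozone T2 each have 2 or 3 patients at 0 of 5, yet every ozone patient scores 3 of 3 at T3. Either fast recovery is real in these data, or there is another fault, such as unscored items entered as 0.

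These points stand. Reversal is one explanation among several, and a blanket recode to 8 minus the score could itself be wrong. They do not remove the need for the check: item 3 of the working still requires suppuration, high oedema or high pain in 28 ozone patients and at least 40 controls, and the tables do not show it.

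**Conclusion.** The concern holds as a question of plausibility that only item-level data can settle; it is not a demonstrated coding error. Given complete scoring and R's default quartiles, the ozone T1 distribution is fixed, and the result under the key is hard to reconcile with T2 and T3.

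The consequence is conditional but large. If all T1 items were reversed, the difference in totals on the phase-mean basis rises from 0.09 to 1.07. It is then below the threshold in section 2.4 ("Statistically significant differences were assessed using two-sided P-values below 0.05") under every SD tried, both arm means move from the acceptable to the excellent band, and the T1 difference (P = 0.006) favours ozone. Partial reversal or unscored items would give other figures.

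The ozone total is a separate matter and does not depend on reversal: 9.24 and 9.37 cannot both be right if all 38 patients were scored at each visit. It does not show which way T1 was coded.

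**What to change.** 1. Check every T1 item in the database against the key, including any unscored item entered as 0.
2. Recode only the items found to be entered against the key.
3. Re-sum the total so that it equals T1 + T2 + T3 for each patient, and reconcile 9.37 with 9.24.
4. Rerun the T1 and total rows, the healing bands and the model for a total above the median. Name the unpaired test in the footnote if that is what was used.
5. If T1 already follows the key, keep it, report the eight T1 items by arm so that suppuration, oedema NRS 6-10 and pain NRS 6-10 are visible, and state that ozone scored worse at day 3-5.

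The cost is a data check and a rerun, with no new data collection. The printed results may change.
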